### ***7.2. Methods and timing for estimating efficacy parameters***

Primary and secondary efficacy criteria will be assessed using appropriate scales (scales are provided in Section 17).

## 8. SAFETY ASSESSMENT

Safety analyses will be based on an assessment of adverse events based on patient complaints and interview, physical examination (including assessment of vital signs) and laboratory results.

All laboratory analyses will be carried out in the sites' local laboratories. Reference ranges of local laboratory normal values will be applied. Prior to the start of therapy (at visit 2), medical events will be recorded to correctly assess the patient's baseline condition.

During screening, information about medical adverse events will be attributed to the patient's medical history

(pre-existing/concomitant illnesses). Clinically significant abnormalities detected by objective examination and laboratory and instrumental examination at screening should not be reported as AEs, but should be recorded as associated pathology. A worsening of the original disease/condition, if it occurred during the trial, should be recorded as an AE.

### 8.1. *Safety parameters*

1. Number of adverse events (AEs)/serious AEs (SAEs).
2. Frequency and severity of AE/SAE associated with Investigational product/placebo.

Patients/patient's parents will be interviewed for adverse events by members of the trial staff at each visit. Spontaneous and identified adverse events will be entered on the Clinical Trial Adverse Event Reporting Form, source documentation and reported in the eCRF. In case of adverse events, the investigator may decide to repeat the clinical examination and/or laboratory tests.

Measurement of vital signs (systolic and diastolic blood pressure, HR, RR) will be performed at all visits (except the randomisation visit).

Physical examination will be performed at visits 1, 5, and 6.

Complete blood count will be performed at visits 1 and 5.

Biochemical blood tests will be performed at visits 1 and 5.

Clinical urinalysis will be performed at visits 1 and 5.

### 8.2. *Adverse events*

#### 8.2.1. *Definition of adverse events*

An adverse event (AE) is any adverse change in the health status of a patient or subject of a clinical trial to whom a medicinal (investigational) product has been administered, regardless of the causal relationship with its use. An adverse event may be any unfavourable and unintended change (including a deviation of a laboratory indicator from the norm), symptom or disease, the time of occurrence of which does not exclude a causal relationship with the use of the medicinal product, regardless of the presence or absence of a relationship with the use of the medicinal product.

#### 8.2.2. *Reporting adverse events*

The investigator and members of the trial staff at the Investigational site are responsible for

identifying, providing appropriate medical care, documenting and reporting cases that fall within the definition of adverse events and serious adverse events.

The protocol provides for the recording of all AEs that occur to the patient after the first administration of the trial therapy and until the end of the patient's participation in the trial.

During screening, information about medical adverse events will be attributed to the patient's medical history

(pre-existing/concomitant illnesses).

The planned trial will record all deviations in the health status of patients (based on the results of physical examination, laboratory and instrumental methods of investigation) from the data obtained at the Screening and from the accepted reference values.

After obtaining the necessary information, the investigating physician will categorise the patient's condition as 'normal', 'clinically insignificant abnormalities' or 'clinically significant abnormalities'. In case the abnormalities detected during the trial have not been previously reported, or there is an aggravation of the patient's condition vs. the data obtained at Screening, the detected abnormalities will be classified as AEs.

The patient will be informed by the investigator to report all adverse events that occur during the trial.

Investigators should document all adverse events that were observed in the patient during the trial in medical histories and Case Report Forms. The patient is warned to report any new symptoms they develop to the investigator between visits.

Each individual AE should be described in detail. Regardless of the presumed causal relationship, all adverse events spontaneously reported by the patient, or identified by the investigator and/or members of the trial staff, should be reported on the adverse event form of the eCRF. For serious AEs (SAEs), a SAE form must also be completed.

The registration of an AE is completed according to the results of the examination at the 6th visit.

Records of adverse events should include the following:

- date of the Investigational product therapy start (if applicable);
- date of an AE onset;
- patient identification (initials, age, randomization number in the trial);
- description of the event (symptoms, diagnosis) and its outcome;
- classification (severity, foreseeability, severity, outcome, relationship to drug use);
- measures taken (therapeutic or diagnostic measures prescribed, if applicable);
- description of the results of therapeutic and diagnostic measures (if applicable);
- date the AE resolved.

An additional procedure must be followed for serious AEs (SAEs) (see section 8.4).

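### Every new or worsened abnormality becomes an AE whatever its clinical-significance grade, so total AE counts can be inflated and between-arm contrasts on those totals diluted

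*Protocol*

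**What the plan says.** Protocol 8.2.2 has the physician place each patient in one of three classes: normal, clinically insignificant abnormalities, or clinically significant abnormalities. The sentence that follows sets the AE rule. If findings "have not been previously reported, or there is an aggravation of the patient's condition vs. the data obtained at Screening", then "the detected abnormalities will be classified as AEs". The only filter is novelty or worsening. The synopsis (1.1, statistical methods) repeats this text.

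The AE definition in Protocol 8.2.1, carried into SAP section 10, points the same way: an AE may be any unfavourable change, "including a deviation of a laboratory indicator from the norm". Neither document limits the rule elsewhere.

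The first safety criterion in Protocol 8.1 is the number of AEs and SAEs. The second is "Frequency and severity of AE/SAE associated with Investigational product/placebo". SAP sections 6 and 10 commit to the total number of AEs and the number of patients who have one. Protocol 9.1 compares event rates and safety outcomes with chi-square or Fisher tests. SAP Tables 12 to 14 break AEs down by preferred term, severity and relatedness, and Table 15 gives between-arm p-values by preferred term. None of Tables 12 to 15 uses the clinical-significance grade.

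**The concern.** Some healthy children will fall outside a reference range by chance at any single blood draw. Under the rule as written, each such excursion that was absent at screening is an AE, even if the investigator judges it to mean nothing. These chance events arise at about the same rate in all three arms. They raise the crude AE total and the proportion of children with any AE, and they shrink the difference between arms on those summaries.

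The breakdowns already planned do not repair the totals:

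- **Severity.** Grade 1 in Protocol 8.2.3 includes findings without symptoms, so insignificant flags share the mild column with mild clinical events.
- **Relatedness.** The possible category includes changes that follow dosing in time but have another explanation, and it counts as related. Visit 5 flags come after 42 days of dosing, so many could qualify.

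**Working it through.** **The plan's own figure.** The documents state no AE rate, AE effect size or power for safety. The only usable figure is the arm size, which was set on SNAP-IV (Protocol 9.2). Pooled SD = √[(4.70² + 7.515²)/2] = 6.27. Then n = 2 × 6.27² × (1.96 + 0.842)² / 2.5² ≈ 99, and the t-based version gives 100 (power 80.2%). With 10% dropout, 100/0.9 = 111.1, stated as 111. The figure reproduces, so 111 per arm is used below.

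**Number of laboratory values.** Protocol 4.6.8 lists six blood-count items, and SAP Table 2 shows six differential cell types, giving 12. Chemistry has nine. That makes 21 blood values; 11 urine parameters would bring it to 32. There is one post-baseline draw: "Complete blood count will be performed at visits 1 and 5", and chemistry and urinalysis follow the same schedule.

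**Share of children with a chance laboratory AE.** Let f be the chance that one value is newly flagged at Visit 5 (assumed, 0.5% to 5%). With independent values, q = 1 − (1 − f)^21.

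**Effect on the any-AE comparison.** Assume true clinical AE rates of 5% on placebo and 18% on drug. With background q, the any-AE rate is 1 − (1 − p)(1 − q), that is 1 − 0.95(1 − q) and 1 − 0.82(1 − q). Power (two-sided 0.05, n = 111 per arm) is Φ[(d − 1.96·se₀)/se₁], where d is the difference in rates, se₀ its pooled standard error and se₁ its unpooled standard error.

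Worked case, f = 0.5%: q = 1 − 0.995^21 = 0.100. The rates are 14.5% and 26.2%, so d = 0.117, se₀ = 0.0540 and se₁ = 0.0535. Power = Φ[(0.117 − 0.1059)/0.0535] = Φ(0.208) = 58%.

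| f per value | q | any AE, placebo | any AE, drug | power |
|---|---|---|---|---|
| 0 | 0% | 5.0% | 18.0% | 86% |
| 0.5% | 10% | 14.5% | 26.2% | 58% |
| 1% | 19% | 23.1% | 33.6% | 41% |
| 2.5% | 41% | 44.2% | 51.8% | 21% |
| 5% | 66% | 67.7% | 72.1% | 11% |

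**Relaxing independence.** Blood values move together, and a child who is out of range at screening tends to stay so. A simulation set each value at a 5% chance of being out of range at a visit and counted only values normal at screening and abnormal at Visit 5. With correlation of 0 to 0.3 between values and 0 to 0.8 between visits, 39% to 64% of children had a new flag on the 21 blood values. At q = 0.389 the any-AE rates are 1 − 0.95 × 0.611 = 42.0% and 1 − 0.82 × 0.611 = 49.9%, with power 22%. At q = 0.638 they are 65.6% and 70.3%, with power 11%.

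**A second set of assumed rates.** For 10% against 25%, power is 84% with no background, 64% at q = 0.10, 27% at q = 0.40 and 13% at q = 0.66.

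**Single preferred terms.** Flags coded under laboratory terms do not enter the count for a clinical term. A clinical term at 10% against 25% keeps its 84% power whatever q is.

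**The case against.** A reader might infer that chance flags swamp the safety endpoint and hide a real drug-placebo difference. The documents do not support that. They give no flag rate and no AE rate, and every input in the table except the arm size and the number of values is assumed. The trial was sized on SNAP-IV alone, so no planned safety power is lost. Table 15, where the p-values sit, is laid out by preferred term and has no any-AE row. The general chi-square and Fisher text would permit a test on the totals, but nothing makes it the basis of the safety conclusion. The safety objective also covers severity and nature, not one count. All of this stands, and it limits the point to the totals.

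A reader might also infer that the grade is never used. That is too strong. SAP Tables 8 and 9 separate insignificant from significant deviations for urinalysis and physical examination, and SAP section 10 lists clinically significant haematology findings. But Table 11, which holds the blood values, has no such split, and nothing carries the grade into the AE totals.

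Nor does Protocol section 8 set clinical significance as an AE threshold at screening. It says "Clinically significant abnormalities detected by objective examination and laboratory and instrumental examination at screening should not be reported as AEs", which concerns how baseline findings are filed. Its rule that worsening is an AE agrees with 8.2.2.

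Finally, broad capture is a coherent choice. The definition in 8.2.1 expressly includes laboratory deviations, and Protocol 2.4 says the drug has had no earlier controlled trial in children. Restricting AEs to significant findings would conflict with that definition and could drop a consistent mild laboratory signal from the AE counts. This is a good argument against narrowing the AE definition. It is no argument against reporting the totals both ways.

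**Conclusion.** The point holds for the crude number of AEs and the number of children with an AE. As written, a new finding graded clinically insignificant is an AE, and the planned totals do not separate it from clinical events.

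The loss could be moderate or severe. With 0.5% to 5% new flags per blood value, independent, about 10% to 66% of children would carry a chance laboratory AE. Any-AE power for an assumed 5% against 18% would fall from about 86% to between 58% and 11%. At a 5% out-of-range rate, correlation brings the share of children flagged to 39% to 64%. Urine is left out of these figures and would add to them.

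Single clinical preferred terms and SAEs are not diluted. This is a low-cost improvement in reporting, not a defect that invalidates the safety analysis.

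**What to change.** Leave AE capture in Protocol 8.2.1 and 8.2.2 as it is. In SAP sections 6 and 10 and Tables 12 to 15:

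- Report the number of AEs and the number of patients with an AE twice: (a) for all AEs, and (b) excluding laboratory-only or examination-only findings graded clinically insignificant that had no symptoms and led to no action.
- Make the between-arm comparison of totals on (b).
- List the excluded findings separately by arm, so that a consistent mild shift stays visible.

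No new data are needed: Protocol 4.6.8 already has the physician judge the clinical significance of each out-of-range laboratory value, and 8.2.2 already requires the grade. The cost is one extra split in the AE tables and a second headline count, which the report must explain. The SAP is written for protocol version 3.0 while the protocol is now version 4.0, so the change can go into the same update.

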### **8.2.3. *Determination of adverse event parameters***

According to current guidelines, the parameters of AEa in relation to the variables of severity, foreseeability, severity, outcome and causality will be assessed as follows:

Severity:

CONFIDENTIAL

58

"Serious" adverse event is defined as any adverse medical event that, regardless of the dose of the medicinal product:

- resulted in death;
- was life-threatening;
- has caused severe or permanent disability or incapacity for work;
- required an inpatient admission (other than a previously planned admission) or causes an extension of the current hospitalization;
- resulted in a congenital anomaly/developmental defect;
- required medical intervention to prevent the above conditions;
- there has been transmission of an infectious agent through a medicinal product.

In addition, a serious adverse event includes any event that does not formally fit the above criteria but is a significant medical event from the investigator's point of view.

"Serious" adverse reaction is a serious adverse event with a causal relationship (possible, probable, or credible) to the use of the Investigational product;

All other AEs that do not meet these criteria will be considered as "non-serious".

**Listedness:** Unlisted adverse reaction - an adverse reaction whose nature, severity or outcome is not consistent with the information contained in the investigator's brochure.

**Severity:**

The severity of AEs is assessed as follows:

The investigator assesses the severity of an adverse event according to the Common Terminology Criteria for Adverse Events (CTCAE) current version at the time of the trial. If an adverse event cannot be classified according to the CTCAE criteria, the Investigator will select the closest description of the severity of the adverse event from those given in the classification based on personal clinical experience:

Degree of severity	Category	Definition/Description
1	Mild	No symptoms or mild symptoms, only clinical or diagnostic follow-up is required; no intervention is indicated
2	Moderate	Only minimal, localised or non-invasive interventions are indicated; limitation of daily living activities
3	Severe	Severe or clinically significant but not immediately life-threatening; hospitalization or prolongation of hospitalization indicated; disability; limitation of self-care in activities of daily living
4	Life-threatening/ Disability to work	Life-threatening consequences, urgent intervention required
5	Fatal	Death associated with an adverse event

"Severe" adverse event will not necessarily be "serious" in nature, "serious" adverse event will not necessarily be "severe" by definition.

**Outcome:**

CONFIDENTIAL

59

Protocol version 4.0 dated 15.10.2019.

The outcome of an AE is assessed as follows:

Transition to the SAE:	AE resulted in a condition that meets the criteria of seriousness (resulted in death, was life-threatening, required hospitalization of the patient or its prolongation, resulted in permanent or pronounced disability or incapacity, congenital anomalies or malformations, required medical intervention to prevent the development of these conditions. In case of any unexpected suspected transmission of an infectious agent through a medicinal product has occurred)
Recovery without consequences	The AE has completely resolved without observed residual events
Improved condition	AE in the process of resolution
No change in condition	AE has not resolved
Recovery with consequences	The resolution of the AE has occurred, but the patient still has some residual effects
Death	Patient died due to an AE (death is an outcome, not an AE)
Unknown	The outcome of an AE is unknown because the patient did not show up for the follow-up examination and attempts to obtain follow-up information were unsuccessful (lost for follow-up)

***Relationship to the use of the Investigational product:***

***Determination of the relationship of an AE with the use of the Investigational product***

The association of an AE with the use of investigational products will be assessed using World Health Organisation (WHO) criteria:

- **Definite.** Clinical manifestations of an AE, including abnormalities of laboratory parameters occurring during the period of drug administration, which cannot be explained by the presence of existing diseases and the influence of other factors and chemical compounds. Manifestations of adverse reaction regress after drug withdrawal and occur with repeated administration.
- **Probable.** Clinical manifestations of an AE that include changes in laboratory values that are temporally related to the use of the Investigational product, that are unlikely to be related to comorbidities or other factors, and that regress with drug withdrawal. The response to rechallenge is unknown.
- **Possible.** Clinical manifestations of an AE that include changes in laboratory values that are temporally related to drug administration but can be explained by the presence of comorbidities or the administration of other drugs and chemical compounds. Information on response to drug withdrawal is unclear.

- *Doubtful*. Clinical manifestations of an AE that include changes in laboratory values that occur in the absence of a clear temporal relationship to drug administration; other factors (drugs, diseases, chemicals) are present that may be responsible for their occurrence.
- *Conditional*. Clinical manifestations of an AE involving abnormalities of laboratory indications categorised as 'adverse reactions' that need further data (for accurate assessment) or these obtained data are currently being analysed.
- *Unclassifiable*. Reports of a suspected adverse reaction cannot be evaluated because there is insufficient or conflicting information.

The occurrence of an adverse event will be related to the Investigational product if the relationship is considered by the investigator as definite, probable, possible.

***Physician's actions in relation to the AE:***

1. No action required (continuation of the trial according to the protocol).
2. Reducing the dose, which could mean:
  - reducing the dose of the Investigational product;
  - maintaining a certain dose despite the protocol's request to increase it;
  - reducing the frequency of administration/intake.
3. Cancellation of Investigational product followed by resumption.
4. Complete withdrawal of the Investigational product (complete discontinuation of the Investigational product).
5. Prescribing other treatments, such as:
  - for the treatment of the AE;
  - changing the dosage of the concomitant therapy drug;
  - prescribing non-pharmacological therapy.

***8.3. Continued follow-up period for the AE***

All AEs should be traced to their resolution or until they are deemed by the physician to be "recovered with consequences".

If a serious adverse event occurs, the patient will be monitored until the SAE is resolved by telephone calls to discuss complaints and history, as well as during visits that are not part of the trial schedule but are necessary for patient safety.

If, in the opinion of the attending physician, an adverse event that is not serious requires follow-up of the patient, such follow-up may also be conducted by telephone calls and visits, with questioning of complaints and history.

The Sponsor will report all serious unexpected adverse reactions (hereinafter referred to as SUAR) for the Investigational product identified during the clinical trial to the regulatory authorities:

- no later than 7 calendar days from the date of receipt of information on the identification of SUARs, if they have resulted in death or were life-threatening;
- no later than 15 calendar days from the date of receipt of information on the identification of SUARs for other serious unexpected adverse reactions.

#### **8.4. SAE reporting**

When a SAE occurs, the development of the SAE should be recorded in the source documentation and an SAE reporting form should be completed.

The SAE Reporting Form must be submitted to the CRO/Sponsor representative within 24 hours of the investigators' receipt of the SAE information.

Representative of a contract research organisation (CRO):

[name]

Tel./fax: [name]

E-mail: [mi\\[contact]](mailto:[contact])

Sponsor's Representative:

Qualified Person Responsible for Pharmacovigilance (QPPV) of RPC PHARMASOFT LLC:

[name]

[contact] ext. 162

E-mail: [[contact]](mailto:[contact])

The SAE Reporting Form should be sent even if the investigator has incomplete information on the SAE. Each initial report should contain at least the following information:

- Trial number (identifier or protocol number).
- Patient number.
- Investigator's full name and contact details.
- Description of the adverse event (date of onset, outcome as of the date of the report).
- The result of the investigator's assessment of the seriousness and severity.
- The result of the investigator's assessment of relationship with the Investigational product.

The investigator must receive confirmation that the information has been delivered. An initial report containing incomplete information about a SAE should be immediately followed up with a subsequent detailed written report when new information becomes available to the investigator.

If significant new information is received on an identified SAE, this information should be provided in the form of a follow-up communication. The investigator must comply with the following timelines for sending reports on SAEs to the Qualified Person Responsible for Pharmacovigilance:

- Within 24 hours of being informed of the SAE onset.
- After 30 days, if the SAE is still in progress.
- After the end of the SAE.

Notification to the LEC of all SAE cases at the clinical site is carried out by the investigator within the timeframes specified in the LEC's SOPs.

Where applicable requirements apply, Sponsor will provide appropriate notifications of SAEs to authorized health authorities.

